The purpose of this study is to investigate the usefulness of infusing purified CD34+ cells of donor origin in order to augment graft function in response to declining chimerism after initially performing an allogeneic hematopoietic stem cell transplant (HSCT) for children with primary immunodeficiency diseases. This protocol will be utilized for patients with waning mixed donor chimerism that is inadequate for correction of clinical condition or disease for which stem cell transplant was performed, or for augmentation of immune function. An infusion of selected CD34+ stem cells will be given without any preparative regimen. As the children eligible for this protocol have reduced immune function and pre-existing donor chimerism, we hypothesize that stem cells will be able to engraft and the infusion will augment graft function. This therapy serves as an alternative to a second stem cell transplant that is known to be associated with significant morbidity and mortality. CD34+ stem cells will be collected from the donor used for initial stem cell transplant. Cells will be T-cell depleted (TCD) by performing a CD34 selection using the CliniMACS device (Miltenyi Biotec) in order to prevent development of new or exacerbation of existing graft versus host disease (GVHD), as avoidance of GVHD in nonmalignant diseases is desirable. There is sufficient data showing that mixed donor chimerism is adequate for reverting disease phenotype in certain primary immunodeficiencies. Observations from Europe and CCHMC show that donor chimerism might be boosted by CD34+ stem cell infusion alone without any specific preparative regimen. This therapy is likely to be associated with low toxicity due to the absence of a preparative regimen and lack of exposure to fresh donor cells capable of initiating GVHD, and offers potential significant benefit.

I. PURPOSE OF STUDY

Hypothesis

Mixed or full donor chimerism that is adequate for disease control will be achieved with selected CD34+ stem cell infusion without preparative regimen with minimal or no therapy related toxicity or GVHD.

Objectives

- 1. Assess the toxicity of infusion of donor stem cells in augmentation of graft function in previously transplanted children with immune deficiencies, and bone marrow failures.
- Assess the efficacy of infusion of donor stem cells in augmentation of graft function in previously transplanted children with immune deficiencies, and bone marrow failures.

Endpoints

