Although stem cell transplant from HLA (human leukocyte antigen) identical sibling donor is the most preferable and effective treatment in congenital immunodeficiency diseases, the majority of these patients do not have an available sibling donor and alternative approaches such as T-cell depleted haploidentical parental marrow and matched unrelated donor marrow are used as the only curative option with variable results. As reported by European study from 37 centers in 18 countries (1968-1999), in SCID patients 3 year survival with sustained engraftment was significantly better after HLA-identical than after mismatched transplantation (77% versus 54%) and improved over time ^{1,2}. The outcome for patients with Wiskott-Aldrich syndrome after transplantation, as reported by International Bone Marrow Registry and/or National Marrow Donor Program is significantly influenced by donor type showing the 5 year probability of survival of 87% with HLA-identical sibling donors, 52% with other related donors and 71% (p=0.0006) with unrelated donors ³.

In patients with nonmalignant diseases avoidance of graft versus host disease (GVHD) is most desirable. In some cases use of alternative donor transplant necessitates aggressive graft T-cell depletion that is needed to reduce GVHD. Severe T depletion predisposes these patients to somewhat delayed or incomplete immune recovery and unacceptably high rate of graft failure.

Unlike in malignant diseases where fully ablative conditioning is required to eliminate the tumor, most primary immunodeficiency diseases could be cured with low but sustained levels of donor chimerism ⁴. Compartment specific chimerism after HSCT is commonly reported in SCID with T cells being of donor origin while B, NK and myeloid cells are either from recipient or mixed origin ⁵. For patients with Chediak-Higashi Syndrome (CHS) 12-36% of donor NK cells and T lymphocytes expressing normal CHS1usually is sufficient to treat hematologic manifestations of CHS ^{6,7}. Early mixed chimerism post-transplant is commonly reported in Wiskott-Aldrich syndrome. Chimerism may eventually increase to full donor hematopoiesis in the peripheral compartment and persistent donor chimerism markedly decreases long-term risk of lymphoproliferative disease ^{8,9}.

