Five patients will be enrolled into each stratum for evaluation of graft augmentation. If none of the five patients per stratum show any graft augmentation after one year, accrual to that particular stratum will be closed due to lack of efficacy. Patients will continue to be enrolled into other strata until criteria for five patients per stratum are fulfilled. If one out of five patients per stratum will meet listed criteria for graft augmentation, the next five patients may be enrolled to that stratum. If graft augmentation is seen in 1 of 5 or 2 of 10 cases in any stratum the strategy will be considered worthy of further investigation.

Since initiation of the study, it has been noted that stratum III encompasses a wide variety of diseases and therefore the majority of subjects enrolled have been to this stratum. As at least one subject has met the criteria for improved graft augmentation, the target enrollment for stratum III will be increased to 15 to accommodate this large group of patients.

If the infusion of purified CD34+ donor cells does not increase graft augmentation, patient will be removed from study and treated according to standard procedures.

There are no specific plans at this time to treat the patient with an additional boost of CD34+ cells if graft augmentation does not occur on study. However, this decision will be made on a per case basis as clinically indicated.

2a. Inclusion Criteria

To be eligible for this protocol, patients must have the following:

- 1. Primary immunodeficiency (e.g. SCID, Wiskott-Aldrich and/or other more rare conditions), or a bone marrow failure syndrome with prior allogeneic stem cell transplant.
- 2. Waning donor chimerism or immune function that is inadequate to correct their disease or clinical condition, for which primary transplant was given, as determined by their attending physician.
- 3. Available primary donor.
- 4. Must not have other organ dysfunction deemed by the attending physician to preclude this procedure.

- 5. Age < 35 years at time of transplant
- 6. One of the following must be true:
 - Patients must have evidence of persistent or recurrent immunodeficiency or thrombocytopenia.

-OR-

• Primary immunodeficiency disease with known potential to progress to malignant condition if untreated.

-OR-

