• Debilitating secondary disease known to be a consequence of inadequate immune response to known agent or pathogen, uncontrollable by other available medical therapies (e.g. third patient described on page 5).

2b. Exclusion Criteria

- 1. Absence of an available original donor
- 2. Failure to sign consent form, or inability to undergo informed consent process
- 3. Pregnant or lactating female
- 4. Uncontrolled GVHD

3. **Randomization**

Not applicable.

4. **Procedures**

Pre-infusion evaluation:

Patients enrolled on this protocol will be evaluated for disease status and organ function prior to stem cell infusion, required testing as follows:

- 1. Peripheral Donor Chimerism Studies
- 2. CBC with differential and platelets
- Immunological studies including but not limited to absolute numbers of all lymphocyte subsets NK, T, B lymphocyte function, proliferation to mitogens, immunoglobulins
- 4. Urine pregnancy tests for girls of childbearing age
- 5. Renal and liver function tests

Treatment Plan:

Treatment Scheme

This treatment will involve these steps:

- 1. Pre-infusion evaluation
- 2. Collection of Granulocyte Colony Stimulating Factor (GCSF) mobilized peripheral blood stem cells from same donor used for first transplant as per standard procedures
- 3. Selection of CD34+ stem cells and T-cell depletion using CliniMACS
- 4. Infusion of stem cells into recipient
- 5. Continue monitoring

Schedule*:

Pre-infusion	Clinic visit and evaluation of peripheral blood counts	
Day 0	Infusion of CD34+ selected stem cells	
Day 7	Clinical assessment	
3, 6, 12	Clinical assessment	
months and	Donor chimerism studies	
then yearly for	Immunological studies	
up to 3 years		
post infusion		

*For details see Required Observations, page 10.

Additional testing such as disease specific markers (CD132, WASP) or more frequent testing might be needed at attending physician discretion if indicated by patient's clinical condition.

Preparative therapy:

No preparative therapy or additional immunosuppressive therapy will be given in preparation to stem cell infusion.

Stem Cell Infusion:

Stem Cells will be administered per standard institutional protocols.

Immune Suppression after stem cell infusion:

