Appropriate immunologic studies relevant to indications for CD34 infusion will be performed for stratum II and stratum III patients (see strata on page 6) at three months (+/- four weeks) and at or around six, twelve months and annually for up to 3 years post infusion. These tests will include, but not be limited to, lymphocyte subsets, T cell activation and NK function.

Additional testing like disease specific markers (CD132, WASP) or more frequent testing might be needed at attending physician discretion if indicated by patient's clinical condition.

5. Blood Specimens

Not applicable

6. Other Previously Approved Research Studies In Which The Projected Patient Population May Also Be Involved (include what precautions will be taken to avoid any cumulative risk, e.g., repeated blood sampling, radiation exposure, etc.)

Patients eligible for this study may beeligible for other open therapeutic studies at CCHMC. Study options will be discussed and decided on a case-by-case basis.

7. Data Analysis/Statistical Considerations

Primary Endpoints

The primary endpoint of the study is augmentation of graft function. Graft function will be measured in two ways: firstly the percentage of donor chimerism, and secondly immune function.

Successful augmentation of graft function will be achieved if:

- Donor chimerism is doubled compared to the value immediately pre-infusion at 3, 6, and 12 months, -OR-
- Improvement in immune function studies compared to baseline levels can be documented at 3, 6, and 12 months. Example of immune function studies which would be used would include quantitation of T and B cells and functional studies (mitogens and Immunoglobulin levels). In the case of Wiskott-Aldrich syndrome, improvement of platelet count to >20,000/L without transfusions on 2 separate occasions at least three months apart will be considered successful graft augmentation. Children requiring graft augmentation for a specific limited immune defect, e.g. inability to clear papilloma virus will also be assessed by

clinical response of the infection; resolution or >50% improvement in infection will be considered successful graft augmentation.

Secondary Endpoints

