Infusional Toxicity: Infusion of stem cells could result in infusion reaction presenting as shortness of breath, fever, or anaphylaxis. To reduce the risk of infusion reaction, CD34+ stem cells will be highly T-cell depleted. While we have the expectation of a low occurrence of this toxicity, we will monitor for the frequency and characteristics of infusion related toxicities.

Statistical Analysis

We expect the frequency of adverse events in this study to be low (likely less than 5% events). We will therefore use all 45 patients to determine the frequency of adverse events as our ability to correctly define the frequency of events in any one stratum of 10 cases is low.

Descriptive statistics will be compiled on responding and non-responding cases, including patient and graft characteristics that might influence response. It is recognized that this portion of the analysis is exploratory due to the small sample size, but these data will be used to inform the design of future studies.

Stopping Rules

The primary endpoint of this study is qualitative graft augmentation. Five patients will be enrolled into each stratum for evaluation of graft augmentation. If none of the five patients per stratum show any graft augmentation, accrual to that particular stratum will be closed due to lack of efficacy. Patients will continue to be enrolled into other strata until criteria for five patients per stratum are fulfilled. If one out of five patients per stratum will meet listed criteria for graft augmentation, an additional five patients may be enrolled to that stratum.

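### The chimerism limb of the primary endpoint requires doubling of a percentage, so a patient who starts above 50% donor cannot meet it even by becoming fully donor

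*Combined protocol and SAP*

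**What the plan says.** Section 7 (Data Analysis/Statistical Considerations), Primary Endpoints, gives two limbs joined by OR. The chimerism limb is met if "Donor chimerism is doubled compared to the value immediately pre-infusion at 3, 6, and 12 months". No absolute level, minimum gain or separate rule for high baselines is attached. The second limb accepts improvement in immune function studies, a platelet rule for Wiskott-Aldrich syndrome, or a clinical response of a specific infection.

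The hypothesis in section I is worded differently: "Mixed or full donor chimerism that is adequate for disease control will be achieved".

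Entry does not set a chimerism figure. Inclusion criterion 2 asks for "Waning donor chimerism or immune function that is inadequate to correct their disease or clinical condition", as judged by the attending physician. Under Required Observations, follow-up chimerism is measured only in patients infused because their chimerism was inadequate, and immunologic studies are required for strata II and III.

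The endpoint drives decisions in very small groups. With no responder among the first five, "accrual to that particular stratum will be closed due to lack of efficacy" (Stopping Rules). The enrolment text before the inclusion criteria sets the bar for further interest: "If graft augmentation is seen in 1 of 5 or 2 of 10 cases in any stratum".

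**The concern.** A rule defined as a multiple of baseline behaves badly on a bounded scale. The higher a patient starts, the larger the rise required, until no rise is enough. A patient who reaches the best possible chimerism result can therefore be scored as a failure on the limb meant to measure it.

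One patient matters here because the first decision in a stratum turns on whether there are zero responders or one. If the only responder among the first five started above 50% and had no other route to success, the stratum would close for lack of efficacy when it should have continued.

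At the other end the rule has no floor. A patient can double and remain at a very low level, so meeting the limb does not by itself show the adequate chimerism that the hypothesis speaks of.

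**Working it through.** The plan states no response rate, power or error rate for this criterion, so there is no figure of its own to reproduce.

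**Ceiling.** Input: the doubling rule and a scale capped at 100. For baseline b (in percent) the required value is 2b, attainable only if 2b ≤ 100, that is b ≤ 50.

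| Baseline | Value needed | Attainable |
|---|---|---|
| 25% | 50% | yes |
| 40% | 80% | yes |
| 45% | 90% | yes |
| 50% | 100% | only as full donor |
| 51% | 102% | no |
| 60% | 120% | no |
| 75% | 150% | no |

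This holds whether doubling is needed at all three visits or at any one; the text does not settle which.

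**Low end.** From 5% the rule is met at 10%. The only sufficiency figure in the available text, in section II for Chediak-Higashi syndrome, is "12-36% of donor NK cells and T lymphocytes expressing normal CHS1usually is sufficient". Since 2b < 12 when b < 6, an exact doubling from any baseline below 6% ends under the bottom of that range and still counts. The figure is for one disease and for particular cell types, so it illustrates the gap and is not a threshold for this endpoint.

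**Effect on closing a stratum.** Assumptions, none of them in the documents:
- each patient independently has probability r of a real chimerism response;
- responders at or below 50% do double;
- h of the first five patients start above 50% and cannot score;
- no other route applies to anyone.

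Then P(0 of 5) = (1 − r)^(5 − h).

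| r | h = 0 | h = 1 | h = 2 |
|---|---|---|---|
| 0.2 | 0.8^5 = 32.8% | 0.8^4 = 41.0% | 0.8^3 = 51.2% |
| 0.3 | 0.7^5 = 16.8% | 0.7^4 = 24.0% | 0.7^3 = 34.3% |
| 0.5 | 0.5^5 = 3.1% | 0.5^4 = 6.2% | 0.5^3 = 12.5% |

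These are upper-end illustrations. Any other route to success shrinks the increase, and with h = 0 there is none.

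**Noise cost of a repair.** One candidate for b > 50 is that the recipient fraction at least halves, so the donor value must reach 50 + b/2: 80% from 60%, 90% from 80%. False success was simulated with no true change, independent normal error at baseline and at each visit, values limited to 0–100, and an assumed assay SD of 5 points (the documents give no assay precision).

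| True level | All three visits required | Any one visit suffices |
|---|---|---|
| 80% | 0.04% | 10% |
| 85% | 0.3% | 23% |
| 90% | 1.7% | 42% |
| 95% | 6.3% | not used |
| 97% | 9.6% | not used |

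With SD 3, the all-visits figure at a true 90% is about 0.2%. Under the doubling rule, false success at these levels is zero because success is impossible.

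**The case against.** The strongest reply is about reach. Chimerism is followed only in patients infused because it was inadequate, section II says that low sustained levels can cure most of these diseases, and waning chimerism is described there with a high share of recipient cells. Baselines above 50% may be rare. The strata definitions were not in the text available for review and could narrow the range further. This stands: the number affected cannot be known from the documents.

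Next, the endpoint has other routes. Most patients enter with an immune or platelet deficit, or an infection, that the second limb may score, and section I also mentions white cell and platelet numbers and viral clearance. A reader might infer that success on the primary endpoint is impossible above 50%. The documents do not support that, because of the OR. The rescue is only partial, however. Section 7 does not repeat the general blood-count route, the platelet rule is for one disease, and Required Observations asks for immunologic studies only in strata II and III (the schedule table lists them without that limit).

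Third, a reader might infer that every stratum is at risk of wrongful closure. The enrolment text says that at least one stratum III subject has met the criteria and raises that stratum's target to 15, so it can no longer close at 0 of 5.

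Last, a reader might call the missing floor an error. A relative rise is a coherent measure of augmentation in an exploratory study. What remains is a limit on interpretation.

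**Conclusion.** The point holds for the chimerism limb. From above 50% donor it cannot be met, and from 50% only full donor chimerism meets it. This is arithmetic and needs no assumption. It conflicts with a hypothesis that names full donor chimerism as a success.

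The practical effect is conditional. It needs a patient above 50%, a real chimerism response, no other route that scores it, and a stratum still within its first five patients. The closure percentages also rest on assumed response rates and should not be read as an estimate for this trial. At the low end, meeting the limb shows a rise but not adequacy.

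Whether this should be fixed or only considered depends on how many patients start above 50%. The sponsor can count them, because pre-infusion chimerism is already required.

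**What to change.** 1. Keep doubling for baselines at or below 50%.
2. For baselines above 50% and below 100%, add an attainable criterion, fixed before those patients' data are examined. Examples are recipient fraction at least halved, or full donor chimerism by the laboratory's own definition.
3. State that the criterion must hold at all of the 3, 6 and 12 month visits. Under an any-visit reading, noise near the ceiling would produce many false successes.
4. Report results under the doubling rule alongside. Label any patient already scored whose status changes as rescored after the fact.
5. Tabulate baseline and achieved donor chimerism by stratum for every patient assessed on this limb, responders and non-responders. This lets readers see both low-level doublings and large rises that fell short.

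The cost is an amendment to the endpoint wording and one table. No test is added: the pre-infusion evaluation already includes "Peripheral Donor Chimerism Studies", follow-up chimerism is already scheduled for these patients, and the analysis section already promises that "Descriptive statistics will be compiled on responding and non-responding cases".

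The downsides should be stated. The added criterion is a convention with no basis in the documents. The halving version still allows some false success at very high baselines, about 1.7% at a true 90% and 6% at 95% for SD 5 with all visits required. It also creates a step at the boundary: 100% is needed from 50%, but 50 + 51/2 = 75.5% from 51%. The full-donor version largely avoids that step but is harder to meet.

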The primary endpoint of the study is augmentation of graft function. Graft function will be measured in two ways. Firstly the percentage of donor chimerism, and secondly measured improvement in immune function; improvement in numbers of circulating white blood cells and/or platelets, and/or clearance of opportunistic viral infections.

 Improvement in immune function studies compared to baseline levels can be documented at 3, 6, and 12 months. Immune function studies will include quantitation of T and B cells and functional studies (mitogens and immunoglobulin levels). In the case of Wiskott-Aldrich syndrome, improvement of platelet count to >20,000/L on 2 separate occasions at least three months apart will be considered successful graft augmentation. Children requiring graft augmentation for a specific limited immune defect, e.g. inability to clear papilloma virus will also be assessed by clinical response of the infection; resolution or >50% improvement in infection will be considered successful graft augmentation.

The secondary endpoint is to determine the frequency and characteristics of potential infusion-related toxicity. Experience at our center, using CD34+ selected cells has shown infusion-related toxicity has occurred at an incidence of < 10% (zero toxicity in 9 patients participating in CCHMC IRB study # 2008-0777). While there is little expectation of infusion-related toxicity, the incidence of infusion-related reactions will be recorded and evaluated.

II. SIGNIFICANCE OF STUDY IN RELATION TO HUMAN HEALTH

Primary or congenital immunodeficiency diseases result from inborn genetic defects of the immune system frequently manifesting itself as recurrent and chronic infections and

commonly lead to lethal complications. Currently, more than 100 immunodeficiency diseases have been identified and classified according to the area of immune system that is compromised. Most of these have been molecularly defined and are due to single gene defects.

Allogeneic hematopoietic stem cell transplantation is the only curative approach to date for most of the lethal immunodeficiency diseases including severe combined immunodeficiencies (SCID), T-cell immunodeficiencies, Wiskott-Aldrich syndrome, Chediak-Higashi syndrome and others, where it restores immune function and decreases risk of long term complications such as malignant transformation.

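### The general immune-function limb of the primary endpoint sets no minimum change and no deciding test, and Sections I and IV.7 define success differently

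*Combined protocol and SAP*

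**What the plan says.** The primary endpoint is defined twice in current text: under Endpoints in Section I and under Primary Endpoints in Section IV.7. Both contain the general immune criterion, "Improvement in immune function studies compared to baseline levels can be documented at 3, 6, and 12 months", with no size attached. Section I says of the tests that "Immune function studies will include quantitation of T and B cells and functional studies" (mitogens and immunoglobulins are named). IV.7 offers the same tests as an illustration: "Example of immune function studies which would be used would include quantitation of T and B cells and functional studies".

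The other limbs in IV.7 do carry thresholds. The alternative limb, joined by OR, is "Donor chimerism is doubled compared to the value immediately pre-infusion at 3, 6, and 12 months". Wiskott-Aldrich patients need platelets above 20,000 twice, at least three months apart. For a specific limited defect, "resolution or >50% improvement in infection will be considered successful graft augmentation".

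The two definitions differ in two places:

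- IV.7 requires the Wiskott-Aldrich platelet counts to be reached without transfusion. Section I does not, and Support therapy in Section IV.4 permits blood products.
- Section I counts improved white cells and/or platelets as graft function, with no minimum. IV.7 omits this apart from the Wiskott-Aldrich rule, although inclusion criterion 1 admits marrow-failure patients.

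On testing, the pre-infusion list reads "Immunological studies including but not limited to absolute numbers of all lymphocyte subsets NK, T, B lymphocyte function, proliferation to mitogens, immunoglobulins". At follow-up, "Appropriate immunologic studies relevant to indications for CD34 infusion will be performed for stratum II and stratum III patients", and "These tests will include, but not be limited to, lymphocyte subsets, T cell activation and NK function".

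On decisions, the accrual text before the inclusion criteria closes a stratum at 0 of 5 after one year, allows five more patients at 1 of 5, and treats 1 of 5 or 2 of 10 as enough to pursue the strategy. It raises the stratum III target to 15, noting that at least one subject there met the criteria. It does not say which limb that subject met.

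**The concern.** A laboratory value re-measured three times can exceed its baseline every time without any treatment effect. With no minimum change, such a patient is a responder. With several tests and no rule on which decides, there are more ways for this to happen, and the choice of test can be made after the results are known. There is no control arm against which to judge the chance rate, and one responder in five is enough to carry a stratum forward, so the definition of a single responder settles the result.

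The conflict between the sections adds a second source of misclassification. A transfused Wiskott-Aldrich patient, or a marrow-failure patient whose counts rise, can be a success under one section and not under the other.

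**Working it through.** **Plan figure.** The available text states no null or target response rate, error rate or power, so there is no operating characteristic to reproduce. What can be calculated is how often the criterion is met by chance.

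**Inputs from the documents.** Three follow-up visits (3, 6 and 12 months); no minimum change; decision points of 1 of 5 and 2 of 10.

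**Assumptions, not in the documents.** No treatment effect; independent normal noise with SD 1 at baseline and at each visit; the same single test must exceed baseline at all three visits; every patient in the stratum is scored on this limb; drift as listed below.

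**Formulas.** Let b be the observed baseline, d_j the expected change at visit j, and m the required minimum rise, all in noise SDs.

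- Per patient: p = ∫ φ(b) × ∏_j Φ(d_j − b − m) db. With stable values and m = 0 this is the chance that baseline is the lowest of four exchangeable values, so p = 1/4.
- Stratum reaches 1 of 5: 1 − (1 − p)^5.
- Stratum reaches 1 of 5 and then 2 of 10: P(X ≥ 2) + P(X = 1) × [1 − (1 − p)^5], with X ~ Bin(5, p).

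**Worked case, mild decline** (0.25, 0.5 and 1 SD below the starting level at the three visits): p = 0.1176. Then 1 − 0.8824^5 = 0.4649; P(X = 1) = 0.3564; P(X ≥ 2) = 0.4649 − 0.3564 = 0.1085; both rules = 0.1085 + 0.3564 × 0.4649 = 0.274.

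| No-effect scenario, m = 0 | Patients falsely successful | Strata reaching 1 of 5 | Strata reaching both |
|---|---|---|---|
| Decline 0.25, 0.5, 1 SD | 12% | 46% | 27% |
| Twice that decline | 4% | 18% | 4% |
| Stable values | 25% | 76% | 67% |
| Expected baseline 0.5 SD low | 39% | 92% | 90% |
| Any of four tests may count (correlation 0.5, stable) | 53% | 98% | 98% |
| All four tests must rise (same model) | 4% | 20% | 6% |

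The four-test rows come from simulation, the others from numerical integration.

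The fourth row shifts the mean of the baseline by 0.5 SD and keeps its noise, as when patients tend to be enrolled at a low point. It is not the case of one observed baseline that happens to lie 0.5 SD low, which gives Φ(0.5)^3 = 0.6915^3 = 33% of patients.

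**If only part of a stratum depends on this limb** (stable values, no false success elsewhere): with 2 of the five patients, 1 − 0.75^2 = 44% of strata reach 1 of 5; with 3, 1 − 0.75^3 = 58%.

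**The case against.** The strongest reply is that these patients are declining. Inclusion criterion 2 requires waning chimerism or immune function, so stable values are a poor default and chance success should be rarer. This stands, and the declining models are the ones to lead with. The milder decline still passes 46% of strata at 1 of 5, while the steeper one brings it to 18%. The wide range reflects inputs that the documents do not give.

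Second, follow-up tests are already tied to the indication for infusion. That also stands and makes the any-of-four row an upper case. But the tie governs which tests are performed; nothing says that the indication test decides success.

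Third, a pass leads only to five more patients or to further study. That limits the harm but does not make a pass interpretable. The exploratory label in IV.7 belongs to the descriptive comparison of responders and non-responders, not to the success rule.

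Fourth, the strata list is not in the available text. A threshold there cannot be excluded, and the share of patients relying on this limb is unknown. IV.7 nevertheless sets out the success criteria and refers to no further threshold.

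A reader might also infer more than the documents support:

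- Immunoglobulins are missing from the follow-up test list, but that list is expressly open, so nothing is contradicted.
- Chimerism follow-up is limited to patients boosted for inadequate chimerism. That matches measurement to indication, and the other patients keep the immune limb.
- The stratum III increase cannot be called a chance result, because the limb met is not stated.
- The general immune limb is not the only criterion without a threshold: it is the only one within IV.7, but the blood-count wording in Section I has none either.

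**Conclusion.** The concern holds in this form. The general immune limb accepts any rise over baseline and does not say which test decides, while a single responder in five can carry a stratum. Under one-test, no-effect models with all patients scored on this limb, false success runs from 4% to 39% of patients and from 18% to 92% of strata at 1 of 5. Letting any of four tests count raises these to 53% and 98%. These are ranges under assumed noise and drift, not estimates of this trial's error rate; in particular, the stable-value 76% should not be read as the plan's false-pass rate. What they show is that the same wording can make a no-effect stratum pass seldom or nearly always.

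The conflict between Sections I and IV.7 rests on no modelling: the two texts can classify the same patient differently. The sponsor should correct both matters. Confidence in the size is moderate, because assay variability and the strata composition are not available.

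**What to change.** 1. Reconcile Sections I and IV.7 into one success definition. State whether transfusion-supported platelet values count, and whether blood-count improvement counts for marrow-failure patients. The sponsor decides which text governs.
2. For the general immune limb, make the deciding measure the one that was the indication for the boost, recorded before infusion and tested at baseline and at 3, 6 and 12 months. Require a pre-stated minimum rise over baseline at all three visits, set by the sponsor from assay or within-patient variability. Report other immune tests descriptively.
3. For patients already infused, take the deciding measure from the indication documented at enrollment and re-score without regard to results. Report responders under both the present wording and the single definition. State which limb each responder met, including the stratum III responder behind the increase to 15.

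For illustration, with one test, no effect and stable values (patients; strata at 1 of 5; strata at both rules):

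- A 1 SD minimum gives 7%, 30%, 12%.
- A 2 SD minimum gives 1%, 5%, 0.4%, or 3%, 14%, 2.5% if the expected baseline is 0.5 SD low.

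The cost is endpoint wording, one case report form field, a variability figure per candidate test, and the re-scoring. Indication-relevant follow-up tests are already scheduled in strata II and III. If only assay variability is available, within-patient variation will be understated and false success will exceed these figures. Sensitivity falls: a true 2 SD rise passes in 55% of patients with a 1 SD minimum and 25% with a 2 SD minimum, so the response rate will be lower.
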